5.1.2 Assessment of efficacy

The skin condition will be assessed by using the Generalized Pustular Psoriasis Area and Severity Index (GPPASI), Generalized Pustular Psoriasis Physician Global Assessment (GPPGA) and the CGI-Improvement (CGI-I). Patients' questionnaires will also be used, fatigue scale (FACT-Fatigue), Pain VAS, Psoriasis Symptom Scale (PSS) and other relevant scores as described in [Section 5.1.1](#).

Methodological details for the evaluation of the scores/index are described in the ISF.

Generalized Pustular Psoriasis Area and Severity Index (GPPASI)

The GPPASI is an adaptation for GPP patients of the PASI, an established measure of severity and area of psoriatic lesions in patients with psoriasis [[R96-3541](#)]. Similar adaptions have been used for PPP [[R16-3360](#)]. In the GPPASI, induration component has been substituted by pustules component. It is a tool which provides a numeric scoring for patients overall GPP disease state, ranging from 0 to 72. It is a linear combination of percent of surface area of skin that is affected and the severity of erythema, pustules, and scaling (desquamation) over four body regions.

GPPASI score will be measured at Visits 3 (before study drug administration) to 10, 12 (Day 28), 13 (Day 84), and 14 (Day 140).

Generalized Pustular Psoriasis Physician Global Assessment (GPPGA)

GPPGA relies on clinical assessment of the GPP patient's skin presentation. It is a modified PGA, a physician's assessment of psoriatic lesions, which has been adapted to the evaluation of GPP patients [[R15-5200](#)]. The investigator (or qualified site personnel) scores the erythema, pustules and scaling of all psoriatic lesions from 0 - 4. Each component is graded separately, the average is calculated and the final GPPGA is determined from this composite score. A lower score then indicates a lesser severity, with 0 being clear and 1 being almost clear. To receive a score of 0 or 1, the patient should be afebrile, in addition to skin presentation requirements.

GPPGA score will be measured at Visits 3 (before study drug administration) to 10, 12 (Day 28), 13 (Day 84), and 14 (Day 140).

FACIT-Fatigue scale

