7.3.2 Secondary analyses

The continuous secondary efficacy endpoints, such as GPPASI total score, Pain VAS, and FACIT-Fatigue score at week 2, will be evaluated descriptively, including the original as well as change from baseline values where applicable, along with exact 95% confidence intervals, if feasible. For the GPPASI total score, the percentage change from baseline at week 2 will be displayed.

The binary efficacy endpoint, GPPGA response of 0 (clear) or 1 (almost clear), will be described using patient frequencies and percentages. Exact 95% confidence intervals will additionally be provided for the proportion of patients with a response, if feasible.

The patient set for the evaluation of efficacy endpoints (FAS) will include all treated patients who had a baseline and at least one post-baseline measurement available for either GPPASI or GPPGA. Baseline is defined as the last measurement collected prior to administration of the trial treatment.

Proprietary confidential information © 2016 Boehringer Ingelheim International GmbH or one or more of its affiliated companies

The secondary PK parameters (refer to [Section 5.5.1](#)) will be calculated according to the BI Standard Operating Procedure (SOP) 'Standards and processes for analyses performed within Clinical Pharmacokinetics/Pharmacodynamics' ([001-MCS-36-472](#)). Analyses will be performed for parent drug.

Pharmacokinetic parameters of a patient will be included in the analysis unless the patient has an important protocol violation relevant for the evaluation. Whether a protocol violation is important will be decided no later than in the Report Planning Meeting.

Reasons for exclusion of single pharmacokinetic parameters may be:

- Time deviations
- Use of restricted medications

The patient set for the evaluation of PK endpoints (PKS) will include all treated patients that provide at least one observation for at least one secondary PK endpoint without important protocol violations with respect to the statistical evaluation of PK endpoints. It will be decided in the Report Planning Meeting which patients are to be included in the PKS.

Excluded patients will be listed with their individual plasma concentrations and individual pharmacokinetic parameters, however, will not be included in descriptive statistics for plasma concentrations, pharmacokinetic parameters or other statistical PK assessment.

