7.4.5 Efficacy

The following rules will be used to impute for missing data:

- For continuous endpoints, and for the CGI-Improvement, under the assumption that the disease is self-limiting and will gradually improve over time, the Last Observation Carried Forward (LOCF) approach is intended to be used;
- For binary endpoints, the following will be performed:

Proprietary confidential information © 2016 Boehringer Ingelheim International GmbH or one or more of its affiliated companies

- o If there are data at visits both before and after the visit with a missing outcome, then impute as success only if both neighboring visits also represent a success;
- o Otherwise, impute as a failure to achieve a response (i.e. NRI [No Response Imputation]).

For patients that take a rescue medication during the course of the study, efficacy outcomes subsequent to the time-point at which the medication was taken will be set to missing and will be imputed using the steps described above.

For continuous endpoints, the data will additionally be displayed in the original form without any imputation for missing data performed.

Details on the handling of missing item scores for the FACIT will be based on FACIT Administration and Scoring Guidelines (version 4) and provided in the TSAP.

Further imputation strategies for missing data will be considered in the TSAP.

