#### **4. CHANGES IN THE PLANNED ANALYSIS OF THE STUDY**

The following analyses described in this TSAP are new/adapted analyses from those specified in the revised CTP.

- For secondary efficacy endpoints of a continuous nature, it was specified in the CTP that exact 95% confidence intervals around the mean will be produced. Per specification in [Section 7.5.2.1](#), the 95% confidence intervals for continuous data will be based on the t-distribution.

In the CTP it is stated that analyses of immunohistochemistry and flow cytometry will be conducted. These analyses will not be carried out for the CTR, but may be done at a later time point (depending on the obtained results). In case they are performed at a later time point, the analysis details will be described in a separate document.

In the CTP, it was noted that a logistics plan will be developed to protect the integrity of the trial data once the week 4 analyses has been performed. However, since at this time the final analysis of the efficacy and safety data up to week 4 will be complete, and because no further patient dosing visits are planned, the week 4 results may be made available and published to support enrolment into subsequent trials in this and potentially other indications of BI 655130.

The following analyses described in this TSAP are new/adapted analyses from those specified in the signed version of the TSAP, dated 4 OCT 2017:

- Section 6.2  
Definition of IPV: exclusion criteria 8 (i.e. use of restricted medication prior to the study) was modified from a programmatic to a manual assessment. This was done in order to ensure that medical decision could be made on whether such occurrence of an IPV would or would not affect the assessment on efficacy.

Same consideration was also applied to IPV D2.01 (and D2.02) representing prohibited medication use during the study.

- Section 6.6.2  
LOCF imputation was clarified to confirm that the baseline value would be carried forward in the event of no available post-baseline data (and not just in the case when missing post-baseline data was driven by rescue medication taken immediately after the first dose).
- Section 6.6.9  
Additional imputation strategies, for summary reporting only, are presented for the handling of cases where incomplete data are reported for previous GPP flare occurrences.

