# PV will be detected manually.

Source: BI reference document 'Protocol Violation Handling Definitions' [001-MCS-50-413\_RD-01] (2).

Table 6.2: 1 Important protocol violations (continued)

Category / Code	Description	Comments	Excluded from
B	Informed consent		
B1	Informed consent not available	Date of informed consent missing or no signature on patient's "Declaration of Informed Consent"  In this case: Patient's data will not be used at all.	All
B2	Informed consent too late	Informed consent date was after Visit 1	None
C	Trial medication		
C1	Incorrect trial medication		
C1.01	Study drug medication not taken	Patient entered but no study drug taken	TS, FAS, PPS, PKS, BMS, DSS, RSS
C2	Non-compliance		
C2.01	Non-compliance with study drug intake-- administered dose too high	Study medication dose is greater than 120% of the planned dose	PPS
C2.02	Non-compliance with study drug intake-- administered dose too low	Study medication dose is less than 70% of the planned dose	PPS, BMS, DSS, RSS
D	Concomitant medication		
D1	Previous medication		
D1.01	Washout of previous medication too short	Washout period too short - See Table 4.2.2.1: 1 in CTP	PPS, PKS #
D1.02	Rescue use on or after Visit 2 but prior to administration of study drug	Rescue medication taken on the day of Visit 2 or on the day of Visit 3 (clock time will not be reported)	FAS, PPS
D2	Prohibited medication use		
D2.01a	Use of prohibited med. on or after V2 or during the on-trt. period, unless rescue trt. to stabilize a worsening disease cond. – prior to or on D14, with potential influence on eff. data	See the list of restricted medication in CTP, Table 4.2.2.1: 1, manual assessment of potential influence at RPM/DBLM	PPS, PKS, BMS, DSS, RSS #

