## **6.3 PATIENT SETS ANALYZED**

The following analysis sets will be defined for this trial:

- **Enrolled set (ES):**  
This patient set includes all patients who signed informed consent.  
It will be used for analyses of patient disposition.
- **Entered set (ENT-S):**  
This patient set includes all entered patients (as identified by the investigator in the eCRF), whether treated or not.  
It will also be used for analyses of patient disposition.
- **Treated set (TS):**  
This patient set includes all patients in the ENT-S who received study drug at Visit 3.  
It will be used for analysis of safety data.
- **Full analysis set (FAS):**  
This patient set includes all patients in the TS who had a baseline and at least one post-baseline measurement available for GPPASI or GPPGA without any IPV flagged for exclusion from the FAS in the table above.  
This is the main analysis set for presentation of efficacy.
- **Per protocol set (PPS):**  
This patient set includes all patients in the FAS who adhered to the CTP without any IPVs which are flagged for exclusion from the PPS in the table above.  
The PPS will be used for sensitivity analysis of secondary efficacy endpoints.
- **Pharmacokinetic parameter set (PKS):**  
This patient set includes all patients in the TS who provide at least one observation for at least one secondary PK endpoint, which was not flagged for exclusion. PK parameters (and blood and plasma concentrations) can be flagged for exclusion due to a protocol violation relevant to the evaluation of PK (to be decided no later than in the RPM) or due to PK non-evaluability (as revealed during data analysis, based on the criteria specified below). Exclusion of a patient's data will be documented in the CTR.  
Relevant IPVs are documented in [Table 6.2: 1](#) above.  
Plasma and blood concentrations and/or parameters will be considered as non-evaluable, if e.g. a pre-dose concentration is >5% of the  $C_{max}$  value of that patient, or if relevant time deviations occurred (as identified no later than in the RPM), or due to use of restricted medications (as identified no later than in the RPM).  
**CTP:** *It will be decided in the Report Planning Meeting which patients are to be included in the PKS.*  
This patient set will be used for the descriptive analysis of concentrations and PK parameters.

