### Binary efficacy endpoints

Some efficacy endpoints are defined in terms of the proportion of patients with a particular binary outcome, i.e. achievement of a GPPGA total score of 0 or 1. For those binary outcomes, the different methods for handling of missing data, presented below, will be performed as presented in Table 6.3: 1. Please note that some of these binary outcomes are derived from other parameters, but imputation is planned to take place only at the binary level, i.e., the GPPGA total score itself will not be imputed, but the binary endpoints derived based on these scores will be imputed.

- The following primary imputation strategy ("NRI") will be performed:
  - If there are data at the visits both immediately before and immediately after the visit with a missing outcome, then impute as success only if both the preceding and the following observations also represent a success (independent of whether the preceding and following observations were selected for analysis based on time windows described in [Section 6.7](#));
  - Otherwise, impute as a failure to achieve a response (i.e. no response imputation [NRI]).

For patients who take a rescue medication (as defined in [Section 5.3.4](#)) during the course of the study, all efficacy outcomes measured after the day of first use of rescue medication will be set to missing and, during the on-treatment period, will be imputed using the steps described above.

- Observed cases (OC) approach will be used as a sensitivity analysis and will include all collected data, with no imputation performed on the missing data. Such an OC approach will exclude all values measured after intake of a rescue medication (i.e. such values will be set to missing).
- Observed cases including rescue (OC-IR) approach will be used as a further sensitivity analysis and is an extension of the OC approach which includes additionally all values which were measured after rescue medication intake.

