#### Continuous efficacy endpoints

For continuous efficacy endpoints, such as the pain VAS, FACIT-Fatigue scale score, and GPPASI total score, the different methods for handling of missing data, presented below, will be performed as presented in [Table 6.3: 1](#):

- Imputation technique ("LOCF"): Under the assumption that the disease is self-limiting and will gradually improve over time, the LOCF approach will be used as the primary imputation strategy to replace missing values either at intermediate visits or due to early withdrawal from the trial. The last available value, including baseline, will be carried forward to all subsequent visits within the on-treatment period at which a measurement is missing. Values measured after the day of first rescue medication intake (as defined in [Section 5.3.4](#)) will be set to missing and the missing values within the on-treatment period will be imputed by LOCF.
- In addition, as sensitivity approaches, the OC and OC-IR will also be performed.

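### IPV D1.02 is meant to catch rescue before dosing, but its date-only rule also drops rescue given after the infusion, or at an unknown time, on Day 1 from the FAS

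*SAP*

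**What the plan says.** Row D1.02 of SAP Table 6.2:1 has two parts. Its description limits the violation to rescue from Visit 2 onwards that precedes study drug. Its comment gives the working rule: "Rescue medication taken on the day of Visit 2 or on the day of Visit 3 (clock time will not be reported"). The consequence is exclusion from the FAS and the PPS.

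SAP 6.3 applies that flag. The FAS consists of treated patients with a baseline and a post-baseline GPPASI or GPPGA, "without any IPV flagged for exclusion from the FAS in the table above". It is the main set for efficacy. The FAS in Protocol 7.3.2 carries no violation clause: it "will include all treated patients who had a baseline and at least one post-baseline measurement available for either GPPASI or GPPGA".

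Rescue after dosing has its own handling. Protocol 7.4.5 says that "efficacy outcomes subsequent to the time-point at which the medication was taken will be set to missing and will be imputed". SAP 6.6.2 says for binary endpoints that "all efficacy outcomes measured after the day of first use of rescue medication will be set to missing", followed by non-response imputation (NRI). For continuous endpoints the same values are set to missing, and then "The last available value, including baseline, will be carried forward to all subsequent visits within the on-treatment period at which a measurement is missing".

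**The concern.** The description and the rule of D1.02 cover different patients. The description covers rescue before the infusion. The rule covers the whole calendar day of the infusion, because without a clock time the data cannot separate the hours before dosing from the hours after it.

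A patient who worsens after the infusion and is rescued the same day is a treatment failure under SAP 6.6.2. Under the literal D1.02 rule that patient is not in the main efficacy set at all. Membership of the FAS would then depend on something that happened after treatment, and the exclusion would tend to favour the drug. With 6 to 10 patients planned, one exclusion is visible in the headline proportion and mean, and SAP Section 3 allows the Week 4 results to be published to support later trials.

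**Working it through.** **Step 1. Can post-dose rescue meet the rule?** The protocol flow chart (footnote 2) identifies Visit 3 as the infusion day, and Protocol 6.2.2 places the infusion last among that visit's activities. The hours after the infusion therefore fall on the date that D1.02 flags. Protocol 4.2.1.1 leaves rescue for a worsening flare to the investigator. Its recommended two-week wait concerns patients without improvement or change. Post-dose rescue on Day 1 is unlikely but permitted.

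**Step 2. The texts side by side, for one patient with Day 1 rescue**

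| Timing of rescue on Day 1 | D1.02 description | D1.02 rule | SAP 6.6.2 handling if kept |
|---|---|---|---|
| Before infusion | violation | excluded from FAS | not the intended case |
| After infusion | not a violation | excluded from FAS | NRI failure; baseline carried forward |
| Undetermined | cannot be decided | excluded from FAS | NRI failure; baseline carried forward |

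The second row is the mismatch. The third is the case that the rule settles by exclusion.

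**Step 3. Size for the binary endpoint.** The documents give no figure to reproduce and no rate of Day 1 rescue. Assume exactly one such patient among n treated, with x responders among the others. Kept, the proportion is x/n. Excluded, it is x/(n−1). The shift is x/(n(n−1)).

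- n = 6: 1/30 = 3.3 points (x = 1) to 5/30 = 16.7 points (x = 5)
- n = 8: 1/56 = 1.8 points (x = 1) to 7/56 = 12.5 points (x = 7)
- n = 10: 1/90 = 1.1 points (x = 1) to 9/90 = 10.0 points (x = 9)

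The shift is zero if x = 0. A middle case with Wilson 95% intervals: 5/8 = 62.5% (30.6 to 86.3) becomes 5/7 = 71.4% (35.9 to 91.8), a rise of 5/56 = 8.9 points.

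**Step 4. Size for the mean GPPASI reduction.** Baseline carried forward is a 0% reduction. Let m be the mean reduction in the other n−1 patients. Kept, the mean is m(n−1)/n. Excluded, it is m. The shift is m/n. For assumed m of 30% to 70%:

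- n = 6: 5.0 to 11.7 points
- n = 8: 3.75 to 8.75 points
- n = 10: 3.0 to 7.0 points

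With the t-interval of SAP 7.5.2.1 and n = 8:

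- m = 70, SD 20 in the others: 61.25 (35.4 to 87.1) kept, 70.0 (51.5 to 88.5) excluded
- m = 30, SD 30 in the others: 26.25 (1.4 to 51.1) kept, 30.0 (2.3 to 57.7) excluded

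**The case against.** **The meeting can correct it.** SAP 6.2 requires each deviation to be assessed before it counts as important and lets discrepant values be queried. SAP 6.3 sends exceptional cases to the same meeting. Rescue for worsening is allowed, so a rescue known to be post-dose is outside D1.02 by its description. This stands. A reader might infer that the row forces the meeting to drop such a patient, but the documents do not go that far. What remains is that the working rule points the other way and that undetermined timing is resolved by exclusion.

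**The rule follows a convention.** SAP 6.7 treats date-only measurements on the infusion day as pre-treatment. That rule is about measurements, which at Visit 3 are mostly scheduled before dosing. Rescue is unscheduled. Adverse events, also recorded without a time, go the other way, to the treatment phase (SAP 6.1 and 7.8.1). The convention explains the choice but does not settle it.

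**Protocol retention is not certain.** The FAS needs a post-baseline GPPASI or GPPGA that is *available*. If values set to missing for rescue are not available, a Day 1 rescue patient could fail the FAS without D1.02. This stands, and the fix has to address it.

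**A contradiction with SAP Section 4?** That section speaks of the case where "missing post-baseline data was driven by rescue medication taken immediately after the first dose". Because "GPPASI score will be measured at Visits 3 (before study drug administration) to 10", a reader might infer that the SAP expects Day 1 rescue patients to be analysed and so contradicts D1.02. The documents do not establish this. The phrase is in a log of changes to the previous SAP version. It also fits FACIT-Fatigue and pain VAS, whose first post-baseline assessment is on Day 7, so that rescue on Days 2 to 6 leaves only baseline.

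**Imputed dates.** A reader might also suppose that partial rescue dates, which SAP 6.6.3 can set to the dosing day, would trigger D1.02. The SAP does not say that D1.02 uses imputed dates, so this is conjecture and carries no weight here.

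**Conclusion.** The point holds as a minor defect in one row. Applied as written, D1.02 removes from the main efficacy set a patient whose rescue on Day 1 came after the infusion or cannot be timed, although SAP 6.6.2 has rules for analysing rescue after dosing.

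The reach is narrow: rescue within hours of the infusion. If no rescue is dated Day 1, the effect is zero. If one is, the rise in GPPGA 0/1 lies between 1.1 and 16.7 points over n = 6 to 10 with at least one responder, and the mean GPPASI reduction rises by m/n. The upper ends assume that every other patient responds, and the intervals in the examples overlap widely. Responder counts, means and SDs are assumptions.

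Efficacy is secondary and descriptive. The primary safety endpoint uses the treated set and is unaffected. The exclusion would also be visible in the individual listings and the IPV summary (SAP 7). The rescue definition in SAP 5.3.4 is not in the available text, so it cannot be checked whether same-day medication for an infusion reaction counts as rescue.

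**What to change.** Analysis wording only; rescue management is untouched.

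- Reword the D1.02 comment so that FAS exclusion applies to rescue dated on the day of Visit 2, or dated on the day of Visit 3 and confirmed from source or a site query, before database lock, as given before infusion start.
- Keep Day 1 rescue of undetermined timing in the FAS under the existing NRI and LOCF rules, exclude it from the PPS, and flag it in the display of observed cases including values after rescue (OC-IR).
- State in SAP 6.3 that a collected post-baseline GPPASI or GPPGA counts as available for FAS entry even if it is later set to missing because of rescue.

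The cost is one reworded row, one sentence in 6.3, one flag and an occasional query. The query is practical: there are at most 10 patients, they are inpatients at Visits 2 to 7 (Protocol 6.2), and the infusion start time is recorded (Protocol 4.1.4). In an open-label trial the query should be settled on timing alone.

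The downside is the reverse error. A patient with undocumented pre-dose rescue may count as a non-responder in the main analysis (for example 5/7 = 71.4% becomes 5/8 = 62.5%). In OC-IR that patient's response could be credited to the drug (5/7 = 71.4% becomes 6/8 = 75.0%), which is why the flag is needed. The PPS shows the result without such patients.
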